## 6.4. Medical History/Demographics

Clinically significant medical history (as determined by the Investigator), including history of previous ulcers, characteristics, and duration will be recorded at the time of the Screening.

Demographics and baseline characteristics (including gender, race, ethnicity, and age) will also be recorded at the time of the Screening.

#### 6.5. Physical Examination

The physical examination (PE) will be a complete PE according to the standard at the site and a detailed lower extremity examination at the Screening visit. Physical examinations after the Screening visit may be abbreviated PEs. An abbreviated PE will be conducted at the scheduled study visits: Week -2 (Run-in), Day 1 (Baseline), Week 12, Week 24, and EOS/Early Termination. For participants who continue to receive voxelotor beyond 12 weeks in the Open-label Treatment Period (See Section 5.1), the PE will be conducted every 48 weeks (Appendix 1).

 A complete PE will include at a minimum: Height, weight, general appearance, examination of head, eyes, ears, nose, and throat, skin, cardiovascular and respiratory systems, abdominal examination, neurologic, musculoskeletal, and a detailed lower extremity examination including: vascular—pedal pulses, color of skin, temperature, edema; dermatological—clinical description of the ulcer, skin integrity (calluses, dryness); musculoskeletal—foot deformities such as bunion, hammertoe, bony prominence, fat pad atrophy, altered gait; neurological—absence or presence of sensation, reflexes.

 An abbreviated PE will include at a minimum: Examination of eyes, skin, cardiovascular and respiratory systems, abdominal examination, neurologic, and target ulcer(s) examination.

### 6.6. Vital Signs

Vital signs (blood pressure, heart rate, and temperature) will be measured at every visit during the study, as outlined in the SOA (Appendix 1), after a participant has rested comfortably for at least 5 minutes in the supine or sitting position, as age appropriate and feasible. A repeated measurement of any of the vital signs parameters will be taken within 5 minutes if the first reading is outside the normal range and deemed clinically significant.

#### 6.7. Ulcer Assessments

Target ulcer(s) assessments will be performed by visual inspection and measurement of the surface area by digital photography and will be completed at every visit during the study as detailed in the SOA (Appendix 1). The site will measure target ulcers using digital photographs. The digital photographs taken by the site will be sent to a central external reviewer for review and to determine measurements. The measurements provided by the central external reviewer (not the site) will be used to inform eligibility of participants, and assessment of initial re-epithelialization at the Week 12 visit. In addition, the measurements provided by central external reviewer will be used for assessing study efficacy endpoints.

Further details on these measurements will be provided in the Leg Ulcer Assessment and Measurement Manual.

#### 6.8. Adverse Events and Concomitant Medications

Adverse events and concomitant medications will be recorded at every visit during the study, as detailed in the SOA (Appendix 1). See Section 7.2 for details regarding AE reporting period for this study.

#### 6.9. Height and Weight

Height will be collected at the Screening visit only and weight will be collected at Screening and Week 12 (Appendix 1).

## 6.10. Laboratory Assessments

All laboratory assessments will be performed through a central laboratory. Hematology and serum chemistry will be collected at the Screening visit, Baseline (Day 1), Week 12, Week 24, and EOS/Early Termination. Serum pregnancy test will be performed at the Screening visit, and a urine pregnancy test will be performed at Baseline (Day 1), Week 6, Week 12, Week 18, and Week 24 in female participants who have experienced menarche (see Section 6.10.3 for more information on pregnancy testing). For participants who continue to receive voxelotor beyond 12 weeks in the Open-label Treatment Period (see Section 5.1), hematology and serum chemistry assessments will be conducted every 12 weeks, and urine pregnancy testing will be conducted every 24 weeks. Refer to the SOA (Appendix 1) for the additional details of laboratory tests.

It is the responsibility of the Investigator or designee to assess the clinical significance of all abnormal clinical laboratory values, as defined by the applicable list of normal values on file (ie, local or central laboratory).

For the purpose of this study, a clinically significant laboratory value will be any abnormal result that, in the judgment of the Investigator, is an unexpected or unexplained laboratory value or if medical intervention or corrective action (transfusion, hydration, initiation of antibiotics, or other concomitant medication) is required. Any abnormal values that persist should be followed at the discretion of the Investigator. All clinically significant laboratory value abnormalities are to be recorded as AEs.

Additional and repeat laboratory safety testing for the evaluation of abnormal results and/or AEs during the study may be performed at the discretion of the Investigator or upon request of the Sponsor; it is preferred for the analyses to be conducted by the central laboratory unless medical need necessitates urgent results reporting. Repeat laboratory testing of abnormal potentially clinically significant or clinically significant results for the screening evaluation of the participant may be repeated at the discretion of the Investigator.

Blood specimens collected at the Day 1 visit and Week 12 visit and found to be inadequate for laboratory testing should be redrawn and submitted for laboratory testing within 7 days of the study visit.

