## 5.8.1. Instructions for Female Participants of Child-Bearing Potential

For female participants of child-bearing potential (post menarche) and sexually active, pregnancy should be avoided by either abstinence from sex/sexual intercourse or the use of highly effective means of contraception for the duration of the study, and for a total period of 30 days after the participant has taken her last dose of voxelotor. Highly effective means of contraception are listed below in Section 5.9. Pregnancy reporting requirements are outlined in Section 1.1.

Female participants who become pregnant during the study will be withdrawn from the study.

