#### 7.5.1. Exposure During Pregnancy

An EDP occurs if:

- A female participant is found to be pregnant while receiving or after discontinuing voxelotor.
- A male participant who is receiving or has discontinued voxelotor inseminates a female partner.
- A female nonparticipant is found to be pregnant while being exposed or having been exposed to voxelotor because of environmental exposure. Below is an example of environmental EDP:
  - A female family member of healthcare provider reports that she is pregnant after having been exposed to voxelotor by all possible routes of exposure, eg, ingestion, inhalation, or skin contact.
  - A male family member or healthcare provider who has been exposed to voxelotor by all possible routes of exposure, eg, ingestion, inhalation, or skin contact, then inseminates his female partner prior to or around the time of conception.

The Investigator must report EDP to the Sponsor or designee within 24 hours of the Investigator's awareness, irrespective of whether an SAE has occurred. The initial

information submitted should include the anticipated date of delivery (see below of information related to termination of pregnancy).

- If EDP occurs in a participant/participant's partner, the Investigator must report
  this information to Pfizer Safety using PSSA regardless of whether an SAE has
  occurred. Details of the pregnancy will be collected after the start of voxelotor
  and until at least 140 days after the last dose.
- If EDP occurs in the setting of environmental exposure, the Investigator must report information to Pfizer Safety using PSSA. Since the exposure information does not pertain to the participant enrolled in the study, the information is not recorded on a CRF; however, a copy of the completed report is maintained in the Investigator site file.

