## Appendix 1. Schedule of Assessments

Period	Screening	Run-in	12-Week	12-Week Randomized Treatment			label Treat mum 12 w	Follow- up/ EOS Visit a, v	Early Termination Visit	
Visit Number (Week)	Visit 1 (Week -6 to - 2)	Visit 2 (Week -2)	Visit 3 (Week 0)	Visits 4-8 b (Week 2-10)	Visit 9 (Week 12)	Visits 10-14 c (Week 14- 22)	Visit 15 (Week 24)	Visit 16-A & onward d (Week 28)	Visit 16-B (Week 28)	
Visit Day	-42 to -14	-14	Day 1	Day 14-70	Day 84	Day 96-154	Day 168	Day 196 & onward	Day 196	
Visit Window	_	+3 days	+ 1 day	±3 days	±3 days	±3 days	±3 days	±5 days	±7 days	_
Informed consent/assent	Х									
HbSS, HbS/β  thalassemia test e	Х									
Inclusion/exclusionf	X	X	Xg							
Medical history	X									
Height and weight	X				Xh					
Physical examination i	X	X	X		X		X	$\mathbf{X}^{j}$	X	X
Vital signs k	X	X	X	X	X	X	X	$\mathbf{X}^{l}$	X	X
Serum pregnancy test m	X									
Urine pregnancy test n			X	X	X	X	X	X°		
Hematology p	X		X		X		X	$\mathbf{X}^{l}$	X	X
Serum chemistry q	X		X		X		X	X 	X	X
PROMIS-43 v2.1 PROMIS-37 v2.0 Pediatric Profile r			X		X		X			
VAS r			Xg		X		X			
PGI-C r					X		X			
CGI-C					X		X			

Period	Screening	Run-in	12-Week	12-Week Randomized Treatment			label Treat num 12 wo	Follow- up/ EOS Visit a,v	Early Termination Visit	
Visit Number (Week)	Visit 1 (Week -6 to - 2)	Visit 2 (Week -2)	Visit 3 (Week 0)	Visits 4-8 b (Week 2-10)	Visit 9 (Week 12)	Visit 10-14 c (Week 14- 22)	Visit 15 (Week 24)	Visit 16-A & onward d (Week 28)	Visit 16-B (Week 28)	
Visit Day	-42 to -14	-14	Day 1	Day 14-70	Day 84	Day 96-154	Day 168	Day 196 & onward	Day 196	
Visit Window	_	+3 days	+1 day	±3 days	±3 days	±3 days	±3 days	±5 days	±7 days	_
Target ulcer(s) assessment s	х	X	Xg	X	X	Х	Х		X	X
SOC	X	X	X	X	X	X	X	X 	X	X
Randomization			X							
Dispense study drugt			X	X	Xu	X		X 		
Collect study drug				X	X	X	X	X 	Xw	X
Dispense dosing diary			X		X					
Collect dosing diary				X	X	X	X		Xw	X
Concomitant medications	X	X	X	X	X	X	X	X 	X	X
Adverse events	X	X	X	X	X	X	X	$\mathbf{X}^{l}$	X	X

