- g. These assessments must be completed before participants are randomized to study treatment.
- Only weight will be measured.
- Physical examinations after the Screening Period may be abbreviated, focused on abnormalities identified on the Screening examination, the target leg ulcer(s), and as related to adverse events.
- Every 48 weeks
- k. Vital signs (heart rate, blood pressure, and body temperature) will be measured after a participant has rested for at least 5 minutes in the supine or sitting position. A repeated measurement of any of the vital signs parameters will be taken within 5 minutes if the first reading is outside the normal range and deemed clinically significant.
- Every 12 weeks
- m. Females of child-bearing potential and postmenopausal females will have a serum pregnancy test at Screening.
- n. Urine pregnancy tests will be performed at scheduled visits for women of child-bearing potential and postmenopausal females. If a urine pregnancy test is positive, the result must be confirmed with a serum pregnancy test. Urine pregnancy test will be performed at Baseline (Day 1), Week 6, Week 12, Week 18, and Week 24 in female participants who have experienced menarche.
- o. Every 24 weeks for women of child-bearing potential.
- p. Hematology assessments will include WBC (with differential), RBC count, Hb, hematocrit, RDW, MCH, MCHC, MCV, platelet count, reticulocyte percentage, and absolute reticulocyte count. Blood specimens collected at the Day 1 visit and Week 12 visit and found to be inadequate for laboratory testing should be redrawn and submitted for laboratory testing within 7 days of the study visit.
- q. Serum chemistry will include sodium, potassium, bicarbonate, chloride, calcium, phosphorus, BUN, creatinine, glucose, bilirubin (total, direct, and indirect), total protein, albumin, ALT, alkaline phosphatase, AST, and LDH.
- r. The PRO assessments will be evaluated when available (pending translation and cultural validation requirements).
- s. Target ulcer(s) assessments will be performed by visual inspection (including the lower extremity examination and detailed description of the target ulcer[s]' characteristics) and measurement of the surface area by digital photography. See the Leg Ulcer Assessment and Measurement Manual for additional details.

Period	Screening	Run-in	12-Week Randomized Treatment				label Treat mum 12 w	Follow- up/ EOS Visit a,v	Early Termination Visit	

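### No pregnancy test is scheduled at Visit 16-B or Early Termination: a minor gap in safety monitoring, largest for women who stop between scheduled tests

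*Protocol*

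**What the plan says.** Protocol Section 6.10 places a serum pregnancy test at Screening and adds that "a urine pregnancy test will be performed at Baseline (Day 1), Week 6, Week 12, Week 18, and Week 24" in females past menarche. For those who stay on voxelotor beyond 12 open-label weeks, "urine pregnancy testing will be conducted every 24 weeks".

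Appendix 1 says the same. Its "Urine pregnancy test" row is marked from Visit 3 through Visit 16-A and is blank under Visit 16-B and Early Termination. Footnote n lists the same time points ("Urine pregnancy test will be performed at Baseline (Day 1), Week 6, Week 12, Week 18, and Week 24 in female participants"), and footnote o gives the later frequency ("Every 24 weeks for women of child-bearing potential").

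Other laboratory work does reach the end visits: "Hematology and serum chemistry will be collected at the Screening visit, Baseline (Day 1), Week 12, Week 24, and EOS/Early Termination". Section 3.3.2.2 puts the EOS/Early Termination visit about 28 days (±7) after last dose.

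Two other sections show that the protocol's interest in pregnancy continues after dosing. Section 5.8.1 requires contraception or abstinence "for a total period of 30 days after the participant has taken her last dose of voxelotor". Section 7.5.1 counts an exposure during pregnancy when "A female participant is found to be pregnant while receiving or after discontinuing voxelotor".

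**The concern.** The duty to report a pregnancy found after discontinuation depends on someone finding it. The visit timed to follow the last dose includes blood tests and an abbreviated examination, but no pregnancy test. A woman who conceives late in dosing, or soon after it, and does not yet know it can leave the study untested.

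The checks that do exist there are adverse-event questioning (Section 7), concomitant-medication recording to 28 days after last dose (Section 5.7.1) and the abbreviated examination (Section 6.5). They may bring out a known pregnancy, or a change in hormonal contraception, but they do not test for an unrecognised one. Sections 5.8.3 and 5.9 acknowledge that effects on the human fetus and on pregnancy are not established, so complete ascertainment has some value. Efficacy is not at stake.

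**Working it through.** The plan gives no figure of its own to reproduce. The check is a reading of the schedule followed by day counts.

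**Step 1: is the test really absent?** Three places were compared.
- Section 6.10 text: Day 1 and Weeks 6, 12, 18 and 24, then every 24 weeks.
- Appendix 1 grid: the urine row stops at Visit 16-A and the serum row is marked at Screening only. The hematology and chemistry rows are marked at both Visit 16-B and Early Termination, so the blank cells are not a column shift.
- Footnotes n and o: the same time points as the text.

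All three agree.

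**Step 2: inputs for the day counts.**
- Nominal days: Week 12 = 84, Week 18 = 126, Week 24 = 168, Visit 16-B = 196 (Appendix 1 and SAP Appendix 2.1).
- Windows of ±3 days, giving [81, 87], [123, 129] and [165, 171] (SAP Appendix 2.1). Window of ±5 days in extended treatment (Appendix 1).
- Post-dose visit: 28 − 7 = 21 to 28 + 7 = 35 days after last dose (Section 3.3.2.2).

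**Step 3: longest time from last scheduled test to last dose.**
- Week 24 completer: test and last dose both at about Day 168, so about 0 days.
- Stopping between Weeks 12 and 24: 126 − 84 = 42 and 168 − 126 = 42 days nominal. With windows, 129 − 81 = 48 and 171 − 123 = 48.
- Extended treatment: 24 × 7 = 168 days nominal. With windows, 168 + 5 + 5 = 178.

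**Step 4: longest time from last scheduled test to the post-dose visit.**
- Week 24 completer: 196 − 168 = 28 days (21 to 35).
- Stopping between Weeks 12 and 24: 42 + 28 = 70 nominal; 48 + 35 = 83 with all windows.
- Extended treatment: 168 + 28 = 196 nominal; 178 + 35 = 213 with all windows.

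**Step 5: what the counts mean.** The figures for women who stop between tests are maxima, reached only by stopping just before the next test is due. The Weeks 12 to 24 figures also assume that the woman attends no later scheduled visit. They are gaps in testing and not in contact, since visits run every 2 weeks to Week 24 and every 12 weeks afterwards.

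Two groups are left out. Women who stop drug before Week 12 but remain in follow-up still reach the Week 12 test (Section 3.2). Participants who move to another source of voxelotor stay on drug, and their final visit is the day of transfer (Appendix 1, footnotes d and v).

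**The case against.** The strongest reply is that no requirement is broken. A 30-day contraception instruction does not imply a test, and drawing blood at a visit does not show that a urine test was needed there. A reader might infer that the protocol contradicts itself. It does not: no passage promises a post-dose test, and the text, grid and footnotes agree.

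The protocol also has surveillance of its own. Section 7.5.1 requires reporting within 24 hours of awareness and collects pregnancy details to at least 140 days after last dose. It also follows each pregnancy to its outcome and the child for 3 months after delivery. Section 6.10 lets the investigator or sponsor request further laboratory tests. A reader might infer that post-dose pregnancies go unrecorded, and these provisions rule that out. They do not close the gap, because reporting begins only with awareness and the further tests are for evaluating abnormal results or adverse events.

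Three further objections stand in part:
- The 168-day figure comes from the 24-week testing frequency, a separate design choice. An end-visit test would not change that frequency, though it would give these women one test after last dose.
- Section 3.2 assures follow-up only to at least Week 12. If women who stop later still attend the Week 18 or Week 24 visit, those tests apply and the 42-day figure does not.
- A test at day 21 to 35 cannot vouch for the whole 30-day contraception period, because it misses conceptions shortly before it.

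It is also tempting to estimate how many pregnancies would be missed, or to suppose that the dose pause of 10 May 2024 (SAP Section 2) left women untested. The documents give neither the number of women of child-bearing potential nor a pregnancy rate, and they do not say what testing followed the pause. Neither inference is supported.

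**Conclusion.** The gap is real and minor. The schedule ends pregnancy testing at or before last dose for women whose next contact is the post-dose visit, while the contraception and reporting provisions run past it. It matters little for Week 24 completers and most for women who stop between tests, up to the nominal 42 or 168 days shown above.

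The reading of the schedule is secure. The size rests on stopping just before a test is due and, for Weeks 12 to 24, on no later scheduled visit being attended. Clinical importance cannot be taken further from these documents. They state a lack of knowledge about fetal effects, not a signal of harm, and they refer toxicology to the Investigator's Brochure. Power, type I error and the primary analysis are unaffected.

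**What to change.** In Section 6.10 and in the Appendix 1 urine-test row with its footnote, add the urine pregnancy test already used in the study at Visit 16-B and Early Termination, for females who have experienced menarche. No other change is needed, since pregnancy reporting for participants and partners is already in Section 7.5.1.

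The cost is one urine test per eligible woman at a visit that already takes place, with no added visit or blood volume. The test would pick up conceptions in late dosing and the early post-dose period. Those shortly before the visit, or after it, would still rely on report.

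The SAP gives last subject last visit as 22 October 2024, so nothing can be changed for this trial's participants. The edit is for any protocol that reuses this schedule.

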## Open-label Treatment Period (minimum 12 weeks $[\pm 3$ -day window for each visit])

At the end of the 12-week Randomized Treatment Period, all participants (with the exception of those demonstrating initial ulcer re-epithelialization at Week 12) will receive open-label voxelotor 1500 mg per day and SOC for a minimum of 12 weeks and target ulcers that failed to heal during the initial 12 weeks will be followed for delayed healing. Assessments will continue to be performed per the SOA (Appendix 1).

Note: Participants who have completed 12 weeks in the Open-label Treatment Period may continue to receive voxelotor as long as they continue to receive clinical benefit that outweighs risk as determined by the Investigator or until the participant has access to voxelotor from an alternative source (eg, through a clinical OLE study sponsored by Pfizer, commercialization of the product, or a managed access program). Participants who do not plan to continue to receive voxelotor from an alternative source should continue to the follow-up period after completing 12 weeks in the Open-label Treatment Period.

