### 6.3. Eligibility Assessment, Inclusion/Exclusion Review

Eligibility assessment will be conducted during Screening and following the Run-in Period, prior to receiving study drug on treatment Day 1. Both at Screening and prior to randomization, the Investigator should determine that the participant is in stable clinical condition at their steady state.

Randomization must occur on the same day as treatment, Day 1 (the first dose of study drug). If a participant is randomized and withdrawn from the study prior to the first dose of study drug, they may not be re-screened.

Pfizer will review eligibility criteria verified by the investigator or qualified designee to confirm that participants meet study eligibility criteria before they are randomized into the study. The randomization approval process will be initiated for a participant after an informed consent document has been signed and the investigator or qualified designee has assessed the participant as eligible. The randomization approval will be based on review of CRF/system data.

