Visit Number (Week)	Visit 1 (Week -6 to - 2)	Visit 2 (Week -2)	Visit 3 (Week 0)	Visits 4-8 b (Week 2-10)	Visit 9 (Week 12)	Visit 10-14° (Week 14- 22)	Visit 15 (Week 24)	Visit 16-A & onward d (Week 28)	Visit 16-B (Week 28)	
Visit Day	-42 to -14	-14	Day 1	Day 14-70	Day 84	Day 96-154	Day 168	Day 196 & onward	Day 196	
Visit Window	_	+3 days	+1 day	±3 days	±3 days	±3 days	±3 days	±5 days	±7 days	_

- t. Study drug will be dispensed at the Day 1, Week 6, Week 12, and Week 18 visits. For participants who continue to receive voxelotor beyond 12 weeks in the Open-label Treatment Period (See Section 5.1), study drug will be dispensed every 12 weeks.
- Participants demonstrating initial ulcer-re-epithelization at Week 12 will continue treatment in their assigned treatment group for an additional 2 weeks to confirm ulcer resolution.
- v. Participants transitioning to a program providing voxelotor through an alternative source will complete assessments on the day they transition to that program. Study drug for this study should not be taken on the day of that visit (dose will be taken on that day as part of the alternative source program).
- w. Only required for participants transitioning to a program providing voxelotor through an alternative source

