## 2.3.2. Treatment Group and Reporting Period for Analysis

In the study schematic in Figure 1. Study Schema, the study period and treatment groups to be included in the primary and open-label analysis.

Efficacy and Safety: Primary analysis (Randomized Treatment Period):

- Treatment groups:
  - Voxelotor: participants randomized to voxelotor.
  - Placebo: participants randomized to placebo.
- Reporting Period:
  - From Day 1 through Week 12 for subjects who either do not achieve confirmed reepithelialization or achieve it before or at Week 12 visit.
  - From Day 1 through Week 14 for subjects who have the initial skin reepithelialization confirmed at Week 12 and then the 14-week visit will be used to confirm resolution.

Day 1 is defined as the date of randomization. The last day (i.e. Week 12 visit or Week 14) of randomized treatment period is defined as the last day entered on the disposition page for end of randomized treatment period.

Efficacy: Open-label analysis (Open-Label Treatment Period):

- Treatment groups:
  - Voxelotor: participants randomized to voxelotor who received at least one dose of voxelotor.

- Delayed voxelotor: participants randomized to placebo during Randomized Treatment Period (through Week 12) and who received at least one dose of voxelotor on or after the Week 12 visit.
- Total: participants who received at least one dose of voxelotor.

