#### Baseline Value

Baseline for all assessments other than laboratory or vital sign parameters, will be defined as the last available pre-treatment value taken on or before the day of randomization and will be used for summary of baseline characteristics and change from baseline analyses, as appropriate.

Baseline for a given laboratory parameter will be defined as the average of all non-missing laboratory values on or prior to the randomization Date.

Baseline for a given vital sign parameter will be defined as the average of all non-missing vital sign value on or prior to randomization Date.

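### The SAP's Days 2–125 laboratory window labels post-dose Day 1 redraws and post-switch placebo samples as Week 12, against its own reporting periods

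*Protocol*

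**What the plan says.** - **Redraws.** Protocol 6.10, repeated in Appendix 1 footnote p, says that Day 1 and Week 12 specimens "found to be inadequate for laboratory testing should be redrawn and submitted for laboratory testing within 7 days of the study visit". Neither place requires the redraw to precede dosing.
- **Scheduled draws.** "Hematology and serum chemistry will be collected at the Screening visit, Baseline (Day 1), Week 12, Week 24, and EOS/Early Termination" (Protocol 6.10). Week 12 is the only scheduled post-baseline draw in the blinded period.
- **First dose.** Protocol 6.3 puts randomization and first dose on the same day, and SAP 2.3.2 states "Day 1 is defined as the date of randomization".
- **Switch to open label.** After the randomized period, "all participants (with the exception of those demonstrating initial ulcer re-epithelialization at Week 12) will receive open-label voxelotor" (Protocol 3.1). Appendix 1 footnote t: "Study drug will be dispensed at the Day 1, Week 6, Week 12, and Week 18 visits". Footnote u covers the exception: participants with initial re-epithelialization at Week 12 "will continue treatment in their assigned treatment group for an additional 2 weeks to confirm ulcer resolution".
- **Baseline.** "Baseline for a given laboratory parameter will be defined as the average of all non-missing laboratory values on or prior to the randomization Date" (SAP 2.3.3).
- **Laboratory windows.** SAP Appendix 2.1 gives Day 1 as [1, 1], Week 12 as [2, 125] and Week 24 as [126, 216]. The general table in the same appendix gives Week 12 as [78, 91].
- **Reporting periods.** SAP 2.3.2 starts the open-label period one day after the Week 12 visit, or one day after the Week 14 visit for participants whose resolution is being confirmed then. SAP 6.6.2 summarizes laboratory shifts by reporting period.
- **Visit definition.** SAP 2.3.3 also defines Study Visit as the nominal visit on the CRF.

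**The concern.** A label of Week 12 should mean a value near Day 84 on the randomized treatment. The laboratory window does not secure that. It admits samples from the first week of dosing, and samples from placebo participants who are already taking voxelotor.

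Three outputs use the label: the Week 12 laboratory summaries (SAP 6.6.2); the point biserial correlations of change in Hb, % reticulocytes, indirect bilirubin and LDH with healing (SAP 6.3); and the safety subgroups by Week 12 Hb and by change in Hb at Week 12 (SAP 6.4.2). The last deserves the most care. SAP section 2 records that dosing was paused because of the overall number of deaths, and a mislabelled Hb can put a participant in the wrong stratum of the SCD-related TEAE and TESAE tables.

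**Working it through.** **1. The plan's own window.** Target Day 84 ± 3 gives [81, 87], the stated protocol range. The midpoint of Days 84 and 168 is (84 + 168)/2 = 126, which matches the 125/126 cut. The lower bound fits no midpoint rule: (1 + 84)/2 = 42.5 would start the window at Day 43, whereas Day 2 is simply the day after Day 1.

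**2. Day 1 redraw.** With the visit on Day 1 and a redraw 1 to 7 days later, the sample falls on Study Days 2 to 8. All of these lie in [2, 125], and they are 84 − 8 = 76 to 84 − 2 = 82 days before target. Under SAP 2.3.3 such a sample cannot be baseline. Baseline then rests on the remaining pre-randomization values, in practice Screening.

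**3. Week 12 redraw.** A visit on Days 81–87 plus 1 to 7 days gives Days 82 to 94, all in [2, 125]. For a placebo participant who switched at the visit, the sample is taken on voxelotor. SAP 2.3.2 dates the same sample in the open-label period, so it is Week 12 by window and open-label by period. Participants covered by footnote u stay on assigned treatment for 2 more weeks, longer than the 7-day redraw limit, so their redraws are not contaminated. In the voxelotor arm the drug does not change.

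**4. Unscheduled samples.** Protocol 6.10 allows repeat testing at discretion. After a switch at the Week 12 visit, the window still includes 125 − 87 = 38 to 125 − 81 = 44 days of open-label treatment. Early Termination samples falling on Days 2–125 also take the label.

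**5. Number affected.** The documents give no redraw rate. Assuming 5–10%, 40 × 0.05 = 2 to 40 × 0.10 = 4 placebo participants would have a Week 12 redraw. This is an upper bound, because it counts footnote u participants and early discontinuers.

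**6. Effect of a Day 1 redraw.** Suppose it shows a fraction g of the true Week 12 change, with g assumed to be 0 to 0.5. The change retained for that participant depends on a selection rule that the SAP does not state:
- first value in the window: g, so 0–50%;
- average of two values: (1 + g)/2, so 50–75%;
- closest to target, or last: 100%.

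If it is the only value, g is retained. With independent 5–10% rates for a Day 1 redraw and a missing Week 12 sample, that happens in 40 × 0.05² = 0.1 to 40 × 0.10² = 0.4 participants per arm.

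**7. Effect of post-switch placebo redraws.** If a share f of placebo values each show a fraction g of the full drug effect, the difference between arms shrinks by f × g. With f = 5–10% and g assumed to be 25–50%, this is 0.05 × 0.25 = 1.25% to 0.10 × 0.50 = 5%. At f = 20% it reaches 0.20 × 0.50 = 10%. The documents give no time course for the first week on drug, so g is an assumption.

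**The case against.** Much of the case on the other side stands.

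- **Reporting periods already separate some of these samples.** Because shifts are summarized by reporting period, a reader who infers that every post-switch redraw simply counts as a placebo Week 12 result goes too far. The window and the period disagree, and the SAP does not say which governs. It is also silent on how a redraw is entered under the CRF nominal visit.
- **A Day 1 redraw need not distort anything.** It matters only if it is selected, averaged in, or the sole value. Nor is baseline contaminated, as a reader might infer: post-randomization values are excluded by definition.
- **The efficacy result is not at risk.** A reader might infer bias in the main comparison. The primary and secondary endpoints are ulcer outcomes and use no laboratory value. The laboratory tables are descriptive, and the correlations are exploratory and reported by treatment group.
- **The upper bound of 125 is an ordinary midpoint choice.** True, but it ignores the change of treatment that falls inside the window.
- **Simply adopting [78, 91] has costs.** It would drop valid Day 92–94 redraws from participants still on blinded drug. A cut at first open-label dose removes redraws mainly from non-healers, which ties missingness to healing in the correlations.
- **Protocol edits come too late.** The last visit was on 22 October 2024, so new site instructions would change nothing.

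What remains is a date rule that can put the wrong treatment or the wrong time under a Week 12 label, with no precedence rule and no rule for multiple values.

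**Conclusion.** The concern holds in a limited form. The Days 2–125 window can label first-week samples and post-switch placebo samples as Week 12, and it conflicts with the reporting periods in SAP 2.3.2. The date arithmetic rests on the documents alone. The size does not: with an assumed 5–10% redraw rate, at most 2–4 of 40 placebo participants have a Week 12 redraw, and fewer of those are on voxelotor once participants with initial re-epithelialization are removed. The resulting dilution of a between-arm laboratory difference would be about 1.25–5% under the assumed response fractions. Discretionary and Early Termination samples could add cases, in a number the documents do not allow one to estimate. This does not threaten the trial's efficacy conclusion, but it should be corrected before the Week 12 Hb subgroups and correlations are interpreted.

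**What to change.** Amend SAP Appendix 2.1 only:

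1. Define the randomized-period Week 12 laboratory value as the sample closest to Day 84, taken no earlier than a stated lower bound (for example Day 78, or the Day 43 midpoint) and on or before the participant's first open-label dose.
2. Keep redraws after Day 91 from participants still on blinded treatment.
3. Assign samples taken after the first open-label dose to the open-label period.
4. Report post-dose samples before the lower bound as unscheduled, and Early Termination samples under their own label.
5. State that this date rule takes precedence over the visit window and the CRF nominal visit.
6. Repeat the affected outputs with the present [2, 125] window as a sensitivity analysis, and count the participants whose value changes.

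The cost is a paragraph of SAP text and a check of sampling dates against dosing dates. A few participants will have no Week 12 laboratory value, mainly non-healers, which is why the sensitivity analysis is needed.
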